9.2 Recording

AE data should be obtained through observation of the subject, from any information volunteered by the subject, or through subject questioning.

All AEs (non-serious and serious) that occur during the course of the study, from the time the subject signs the ICF for the trial until last follow up visit, will be collected and recorded in the e-CRF. Any pre-existing medical conditions or signs/symptoms present in a subject prior to the start of the study (i.e., before informed consent is signed) should be specified in the eCRF. These conditions are considered AEs only if they increase either in frequency or severity once informed consent has been signed. Subsequent to signing an informed consent form, all untoward medical occurrences that occur during the course of the study must be documented on the eCRF. When possible, signs and symptoms indicating a common underlying pathology should be documented as one comprehensive event. Thus, any untoward medical occurrences or unfavorable and unintended signs, symptoms, or diseases that occur in the pretreatment, in treatment, or post treatment period are to be considered AEs and/or SAEs, and consequently recorded and reported as such. Should a non-serious AE become serious, the Investigator will then follow the same reporting procedures as for SAEs.

Each AE will be described by:

- Its duration (start and stop dates).
- Severity grade, as defined in § 9.2.2.
- Assessment of the adverse event relationship to the study treatment
- Any action with study treatment taken as a result of the event.
- Outcome.

All AEs should be followed-up to determine outcome of the reaction. The Investigator should follow up the event until resolution or stabilization of the condition. It is the Investigator's responsibility to assure that the subjects experiencing an AE receive definite treatment for any AE, if required.

Serious Adverse Events:

The Investigator must record all SAEs, including sight-threatening events, occurring at any time during the study regardless of presumed causal relationship, on the Serious Adverse Event form in the eCRF of the Electronic Data Capture (EDC) system within 24 hours of learning of the event; information on the SAE must also be recorded on a specific Non-Carbon Repeat SAE form (included in the Investigator's Site File) and forwarded to Crowsource Drug Safety and Dompé Drug Safety, within 24 hours from first knowledge.

If the Investigator becomes aware of a related serious adverse event occurring to a subject after the treatment of that subject has ended, this event should be reported by the Investigator to Dompé Drug Safety, as further described in § 9.3.1.

9.2.1 Relationship of Adverse Events to the Investigational Product

The Investigator will assess the relationship between the AE and the investigational medication, according to the criteria in Table 3 below:

Table 3: Relationship of the Adverse Event to the IMP

None (Intercurrent Event)	An event that is not and cannot be related to the Investigational Product, e.g. subject is a passenger in a road traffic accident or surgical intervention performed during the study, but planned before subject enrollment into the study
Unlikely (remote)	Relationship is not likely e.g. a clinical event including laboratory test abnormality with temporal relationship to drug administration which makes a causal relationship improbable and in which other drugs, chemicals or underlying disease provide more plausible explanations
Possible	Relationship may exist, but could have been produced by the subject's condition or treatment or other cause
Probable	Relationship is likely, the AE abates upon discontinuation of Investigational Product and cannot be due to the subject's condition
Highly Probable	Strong relationship, the event abates upon discontinuation of Investigational Product and, if applicable, re-appears upon repeat exposure

9.2.2 Severity of Adverse Events

The Investigator will grade the severity of any AE using the definitions in Table 4 below. For each episode, the highest severity grade attained should be reported.

Table 4: Severity of the Adverse Event

Mild	Grade 1 - Does not interfere with subject's usual function (awareness of symptoms or signs, but easily tolerated [acceptable]).
Moderate	Grade 2 - Interferes to some extent with subject's usual function (enough discomfort to interfere with usual activity [disturbing]).
Severe	Grade 3 - Interferes significantly with subject's usual function (incapacity to work or to do usual activities [unacceptable])

9.3 Serious Adverse Event Reporting

9.3.1 Reporting Procedure for Investigators to Dompé Drug Safety Pharmacovigilance and to Cromsource

The Investigator must record and report all SAEs, regardless of presumed causal relationship, to Dompé Drug Safety and to Cromsource Medical Monitor, by e-mail (preferred) or fax within 24 hours from first knowledge of the SAE, to the following addresses:

- by fax through the e-[contact] (linked to Dompé Drug Safety and to Cromsource Medical Monitor).
- or, via e-mail to all following addresses:
 - [contact];
 - [contact]
 - [contact]

Contact details for safety matters are listed below:

Dompé Contact Information

Dompé Drug Safety
[name], Senior Safety Manager
Email: [contact]

Dompé Medical Expert
[name] – Chief Medical Officer Biotech,
Email: [contact]

Early Clinical Development Manager
[name]
Email: [contact]

Cromsource Contact Information

For Pharmacovigilance: [contact]

For Medical Monitor: [contact]

The Investigator should also report information on SAEs that continue after subject has completed his/her participation in the study (whether study completion or withdrawal), unless subject has withdrawn his/her consent. The follow-up will continue with no timelines for related SAEs, while for unrelated SAEs the type and extent of follow-up undertaken will be determined for each individual case and will depend upon the nature, severity and medical significance of the event.

Respective IRB must also be informed of all SAEs according to local specific requirements.

SAE reports will be managed directly by the Dompé Drug Safety department, with Cromsource Materiovigilance And Pharmacovigilance Unit (MVPVU) support for follow-up requests.

Follow-up reports (as many as required) should be completed and e-mailed / faxed following the same procedure above, marking a new SAE form, with follow up Number XX”, duly filled in and signed, within 24 hours from awareness.

Whenever more than one SAE is observed, the Investigator should identify which is the primary adverse event, i.e. the most relevant one. If other events are listed in the same report, the Investigator, along with their relatedness to the Investigational Product, should identify which adverse events are serious and which are non-serious. In any case, the Investigator is requested to record his/her opinion about the relatedness of the observed event(s) with the investigational medication.

Depending on the nature and seriousness of the AE, further information, including copies of appropriate medical records of the subject, as well as results of laboratory tests performed will need to be included in the subjects chart.

Note: If a SAE is considered as not related by Investigator but Dompé/Cromsource consider the event related and unexpected this needs to be reported to Investigator.

If the subject was hospitalized due to a SAE, a copy of the discharge summary is to be forwarded to Cromsource/Dompé as soon as it becomes available. In addition, a letter from the Investigator that summarizes the events related to the case as well as results of any relevant laboratory tests also may be requested. Further, depending upon the nature of the SAE, Dompé may request copies of applicable segments of the subject’s medical records.

For pharmacovigilance purposes, all SAEs should be followed up in order to elucidate as completely and practically as possible their nature and/or causality until resolution of all queries, clinical recovery is complete, laboratory results have returned to normal, stable condition is reached or subject is lost to follow-up. Follow-up may therefore continue until after the subject has completed the study up to 30 days after his/her discontinuation from the study for unrelated SAEs, and without timelines for related SAEs.

Up to the database lock, SAE reports should be reported to Dompé Drug Safety and to Cromsource (MVPVU). New serious adverse event occurring after the site is closed should be reported directly to Dompé Drug Safety.

In line with ICH E2A provisions, although the Investigator does not usually need to actively monitor subjects for AEs once the trial has ended, if the Investigator becomes aware of a SAE occurring to a subject after that subject has ended his/her participation in the study (whether study completion or withdrawal), the SAE should be reported by the Investigator to Dompé Drug Safety. Such “post-study cases” should be regarded for expedited reporting purposes as though they were study reports. Therefore, a causality assessment and determination of expectedness are needed for a decision on whether or not expedited reporting is required.

9.3.2 Conditions that should not be reported as serious adverse events

The conditions listed below, that may require hospitalization of a subject, are not considered to be SAE and shall not be reported as such, but only need to be recorded in the CRF:

- Hospitalizations planned before entry into the clinical study which is part of the normal treatment or monitoring of the studied indication and not associated with any deterioration in condition.
- Hospitalization for routine treatment or monitoring of the studied indication, not associated with any deterioration in condition.
- Hospitalization for treatments, which was elective or pre-planned, for a pre-existing condition that is unrelated to the indication under study and did not worsen.
- Hospitalization for general care not associated with any deterioration in condition.
- Treatment on an emergency, outpatient basis for an event not fulfilling any of the definitions of SAEs given above and not resulting in hospital admission.
- In addition, the following situation shall not be considered SAE:
- Anticipated Disease progression in oncology trials, as applicable.
- Trial end points
- AE that are considered expected as part of the trial treatment (such as standard side effects of chemotherapy in an oncology trial or anticipated AE related to study procedure, unless the frequency or intensity is unusual).
- Abnormal lab values or test results that do not induce clinical signs and/or symptoms and require intervention/therapy, i.e. are clinically significant.

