NOTE: The term disability means a substantial disruption of a person's ability to conduct normal life functions. This definition is not intended to include experiences of relatively minor medical significance such as uncomplicated headache, nausea, vomiting, diarrhea, influenza, or accidental trauma (e.g., sprained ankle) which may interfere or prevent everyday life functions but do not constitute a substantial disruption).

- results in a congenital anomaly/birth defect;
- is an important medical event

NOTE: An important medical event is an event that may not result in death, be life-threatening, or require hospitalization but may be considered a SAE when, based upon appropriate medical judgment, it may jeopardize the subject's well being and may require medical or surgical intervention to prevent one of the outcomes listed in the definitions for SAEs. Examples of such medical events include allergic bronchospasm requiring intensive treatment in an emergency room or at home, blood dyscrasias or

convulsions that do not result in subject hospitalization or the development of drug dependency or drug abuse.

Death shall always be reported as SAE: a death due to progression of disease would not have a causal relationship to the product. The investigator should report the event immediately to the sponsor, but the sponsor will not report the event as expedited to the regulatory authority. Cause of death shall always be specified when known or duly investigated.

Sight Threatening Event

For this study medically important events comprise the following sight threatening events, which are considered to be of special interest and by default are to be reported as SAEs:

- Adverse Events that caused a decrease in visual acuity of >30 ETDRS letters or > +0.6 LogMAR (compared with the last assessment of visual acuity at the last visit) lasting >1 hour
- Adverse Events that cause a decrease in visual acuity to the level of Light Perception or worse lasting >1 hour
- Adverse Events that require surgical intervention (e.g., conventional surgery, vitreous tap or biopsy with intravitreal injection of anti-infectives, or laser or retinal cryopexy with gas) to prevent permanent loss of sight
- Adverse Events associated with severe intraocular inflammation (i.e., 4+ anterior chamber cell/flare or 4+ vitritis)
- Adverse Events that, in the opinion of the investigator, may require medical intervention to prevent permanent loss of sight.

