9.3.4 Reporting Procedure to IRB/IEC and to Regulatory Authorities

In addition to reporting the SAE to the Sponsor and Cromsource, the Investigator must also comply with the requirements related to the reporting of SAEs to the IRB which approved the study. The requirements of IRBs vary from one IRB to another; however, as a minimum requirement, the Investigators must promptly report all suspected unexpected serious adverse reaction (SUSAR) to their IRB.

In line with the Sponsor’s procedure and defined timelines, Dompé and Cromsource shall perform an assessment of the expectedness and the causality of each SAE report received and assess regulatory reportability.

Expectedness will be assessed with respect to the current IB [Reference: 4]: due to the early phase of development, all SAEs will be considered unexpected.

For a SAE reported by the Investigator as not related that is subsequently revised to be related by the Dompé, the Investigator will receive a notification.

Events considered “Possible,” “Probable,” and “Highly Probable” related to the IMP treatment will be reported to appropriate regulatory authorities.

In line with provisions set forth in 21CFR312, Dompé Drug Safety shall notify all participating Investigators in an IND safety report of any suspected adverse reaction that is both serious and unexpected and of potential serious risks, from any clinical trials or any other source, as soon as possible, but in no case later than:

- (a) seven calendar days after becoming aware of the information if the event is fatal or life threatening;
- (b) fifteen calendar days after becoming aware of the information if the event is neither fatal nor life threatening.

The investigator in turn shall notify the relevant IRB.

If the results of an investigation show that an adverse drug reaction not initially determined to be reportable is reclassified as reportable, Dompé Drug Safety shall report such reaction in a written safety report as soon as possible, but in no event later than 7/15 calendar days after the determination is made.

Copies of all correspondence relating to reporting of any SUSAR to the IEC/IRB should be maintained in the Investigator’s Files.

Dompé shall also notify FDA in an IND safety report of potential serious risks, from clinical trials or any other source, as soon as possible after Dompé determines the information qualifies for reporting, in particular shall notify of:

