10 STATISTICS

10.1 Study endpoints

Primary safety endpoints are:

- Incidence of treatment emergent adverse events (TEAEs).
TEAEs are defined as an adverse event (AE), which start after first dose of study treatment. These comprise AEs during the treatment and follow-up period.
- Incidence of treatment emergent adverse events during 1st dose schedule (TEAEs Dose 1).
TEAEs Dose 1 are defined as TEAEs, which start after first dose of study treatment and before administration of the first dose at Treatment Day 2.
- Incidence of treatment emergent adverse events during 2nd dose schedule (TEAEs Dose 2).
TEAEs Dose 2 are defined as TEAEs, which start on/after the first dose at Treatment Day 2 and before Follow Up Day 7 (FU1) visit.

Secondary safety endpoints are:

- Incidence of Follow-Up AEs (FUAE)
FUAEs are defined as TEAEs which start on or after Follow Up Day 7 (FU1) visit visit.
- Incidence of ocular TEAEs by eyes.
- Course of ECG parameters ventricular rate, PR interval, QRS duration and QT interval over all visits.
- Course of vital signs parameters systolic and diastolic blood pressure, pulse rate, respiratory rate and body temperature over all visits.
- Changes from baseline in biochemistry parameters over all visits.
Baseline is defined as the Laboratory assessment of Baseline (D-1) Visit
- Changes from baseline in hematology parameters over all visits.
Baseline is defined as the Laboratory assessment of Baseline (D-1) Visit
- Shift in overall interpretation of urinalysis over all visits. Laboratory assessment at Baseline (D-1) Visit is considered as reference for assessing the shift.
- Course of intraocular pressure by eye over all visits.
- Course of visual acuity score by eyes over all visits
The visual acuity score will be derived as the total numbers of letters, which were read correctly at 4 meter plus the total number of letters read at 1 meter as collected on the eCRF page. When 20 or more letters are read at 4 meters the visual acuity score for that eye is recorded as the number of letters correct at 4 meters plus 30. The subject gets credit for the 30 letters at 1 meter even though they did not have to read them. If no letters are read correctly at either 4.0 meters or 1 meter, then the visual acuity score is recorded as "0."
- Course of LogMAR by eyes over all visits.
The logMAR will be derived as – log (Snellen Equivalent result)
- Course of TFBUT by eye over all visits.

- Course of overall NEI score by eye over all visits.

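### Protocol 9.3.2 takes SAE status away from trial endpoints in a trial whose primary safety endpoints are adverse events, which puts SAE classification and reporting at risk but not the TEAE counts

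*Protocol*

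**What the plan says.** Protocol 9.3.2 has two parts. The first names hospitalisations and outpatient treatment that "are not considered to be SAE and shall not be reported as such, but only need to be recorded in the CRF". The second begins "In addition, the following situation shall not be considered SAE" and has four entries:

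- disease progression in oncology trials, where applicable;
- "Trial end points", with nothing to limit it;
- "AE that are considered expected as part of the trial treatment", illustrated by chemotherapy side effects and by anticipated effects of study procedures, with an exception for events that are unusually frequent or intense;
- "Abnormal lab values or test results that do not induce clinical signs and/or symptoms and require intervention/therapy, i.e. are clinically significant".

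Protocol 10.1 opens its primary safety endpoints with "Incidence of treatment emergent adverse events (TEAEs" and defines a TEAE as any adverse event starting after the first dose. Two further primary safety endpoints count TEAEs in the single-dose and multiple-dose phases.

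Elsewhere, Protocol 9.1 makes death an SAE in all cases and describes sight-threatening events as "considered to be of special interest and by default are to be reported as SAEs". Sections 9.1, 9.2 and 9.3.1 require SAEs to be reported within 24 hours. Section 9.3.3, on exemptions for adverse events, is marked not applicable. Section 9.3.4 states that "due to the early phase of development, all SAEs will be considered unexpected".

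**The concern.** A site that looks up what not to report as serious finds an entry covering the kind of event this trial exists to count. Nothing in either document limits that entry to efficacy outcomes or says which section governs in a conflict. An investigator who follows 9.3.2 could in good faith answer no to the seriousness question for an event that 9.1 calls serious. That answer feeds safety reporting, the halting rule and the SAP's serious-event summaries.

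**Working it through.** No calculation in the plan bears on this point, so the check is a comparison of the texts.

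1. **What the endpoint entry can refer to.** Protocol 10.1 has safety, tolerability, pharmacokinetic and immunogenicity endpoints and none for efficacy. The only endpoints that are events are adverse events: TEAEs overall and by dosing phase, follow-up events, and ocular TEAEs by eye. In a trial with an efficacy event the entry would have a harmless meaning. Here no other kind of event is available for it to cover.

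2. **The literal consequence.** A serious event after the first dose is an adverse event starting after the first dose. It is therefore a TEAE, it counts towards a primary endpoint, and under 9.3.2 it is not an SAE. The chain holds for every post-dose serious event, including deaths and sight-threatening events.

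3. **The opposing text.** Section 9.1 makes both of those SAEs and requires any SAE or sight-threatening event from dosing to the last follow-up visit to reach the sponsor within 24 hours. Sections 9.2 and 9.3.1 repeat the duty for all SAEs. Section 9.3.3 indicates that no exemption applies. The two instructions cannot both be followed literally.

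4. **Effect on TEAE counts.** There is none. The sentence in 9.3.2 that keeps CRF recording belongs to its first part, but 9.2 separately requires all adverse events, serious or not, in the eCRF. TEAE incidence is counted regardless of seriousness (Protocol 10.1, SAP 7.2.6).

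5. **What depends on seriousness.**
   - The 24-hour reports, and the 7- and 15-day safety reports in 9.3.4.
   - The halting rule in 9.9, which needs two SAEs in separate subjects with highly probable causality. If two such events occur and one is classed as non-serious, the count is 2 − 1 = 1 and the rule is not met. There is no data monitoring committee (11.3), and the Safety Committee in 9.9 is formed only after a halt.
   - SAP 7.2.8 takes seriousness from the investigator's eCRF answer. A missing answer is counted as serious, but a recorded no stands.
   - SAP 7.2.8 identifies events of special interest by a box in the eCRF section on SAE criteria. An event not handled as an SAE may never have that box ticked. Blind data review verifies these events, but long after 24 hours.

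6. **The entry on expected events.** Section 9.3.2 lets expectedness decide whether an event is an SAE at all. Section 9.3.4 has the sponsor and CRO assess expectedness on SAE reports already received, and treats every SAE as unexpected. The exception for unusual frequency or intensity narrows the mismatch without removing it.

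7. **The entry on test results.** The sentence can be parsed in two ways. If the negative governs only the symptoms, it exempts symptom-free results that need therapy and are clinically significant. If the negative governs the whole phrase, it exempts results that neither cause symptoms nor need therapy. The second is probably intended. The first would collide with 9.1, where an adverse event that may need medical intervention to prevent permanent loss of sight is an SAE. Protocol 8.7 and 8.12 turn clinically significant laboratory and ocular changes into adverse events, so the two can meet in one finding.

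**The case against.** The strongest reply is that nobody would read the endpoint entry this way. An incidence is a group summary, not an individual event. If each TEAE were an exempt endpoint, the SAE provisions of 9.1, 9.2, 9.3.1, 9.3.4 and 9.9 would have no post-dose content. The specific rules on death and on sight-threatening events are also firmer than one generic entry. This has force. It makes it likely that a careful investigator would follow 9.1, and it rules out treating the literal reading as a forecast. It does not give the entry another meaning in this trial, and no precedence rule settles the conflict.

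Several stronger conclusions that a reader might draw are not supported:

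- That the primary outcome is undercounted. All adverse events are recorded whatever their seriousness.
- That all post-dose SAEs would go unreported. This follows only from the literal reading, which other sections contradict.
- That the entry on expected events opens a clear reporting gap. If the rule in 9.3.4 is carried over, no SAE is expected and the entry catches none. The fault is then inconsistency.
- That the test-result entry does exempt clinically significant findings. The sentence is ambiguous, and this is the weakest of the three.
- That a set of serious-event outputs would be wrong. SAP 10.6.1 makes the detailed serious-TEAE tables and listings conditional on such events being reported, and SAP section 12 lists none separately. What is affected is the lines for serious TEAEs and events of special interest in the overall adverse event summary.

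**Conclusion.** The contradiction is real and should be removed. Section 9.3.2, read as written, withdraws SAE status from serious post-dose events that 9.1, 9.2 and 9.3.1 require to be reported. The exposure is confined to SAE classification and what follows from it: 24-hour and expedited reporting, the halting rule, and the counts of serious TEAEs and events of special interest.

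The documents give no basis for a probability that an SAE would be missed or late. One subject is 1/20 = 5% of the planned active arm, but that is true of any single event and does not measure this defect. The conclusion assumes that no other instruction to the site already settles the matter. The SAP mentions protocol clarifications of 21 May 2018, whose text is not available here; its own list of changes (SAP 3.6) says nothing about SAE reporting. The entries on expected events and test results are secondary and need reconciling, not a separate finding.

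**What to change.** In Protocol 9.3.2:

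- delete the entries on trial endpoints and on oncology disease progression;
- delete the entry on expected events, or reconcile it with 9.3.4;
- reword the entry on abnormal test results so that it has one meaning, consistent with 9.1;
- add a sentence saying that the SAE and sight-threatening definitions in 9.1 prevail over 9.3.2.

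Leave the hospitalisation and outpatient-treatment entries as they are.

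The cost is a clarification letter or a wording amendment. Treatment, design and planned analyses do not change. If events have already been recorded under the present text, those answered as not serious can be checked against 9.1 while still masked, at the blind data review in SAP 8.3.3, which already confirms the sight-threatening events.
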